1.1.2 Secondary Objectives

- Compare the ability of ¹⁸F-DCFPyL PET/CT to detect HCC with standard of care imaging (CT and/or MRI), and ¹⁸F-FDG PET/CT.
- To assess the ability of ¹⁸F-DCFPyL PET/CT imaging to assess treatment response to local therapy.

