2 ELIGIBILITY ASSESSMENT AND ENROLLMENT

2.1 ELIGIBILITY CRITERIA

2.1.1 Inclusion Criteria

- 2.1.1.1 High radiological suspicion of hepatocellular carcinoma (LR4 or LR5 based on the most current version of LI-RADS) with at least one measurable lesion on standard imaging modality (CT and/or MRI).
- 2.1.1.2 Eligible for local therapies (included but not limited to surgical resection, stereotactic radiation therapy, transarterial chem/radio/bland embolization, microwave ablation, radiofrequency ablation).
- 2.1.1.3 Ability to take oral medication and be willing to adhere to the study intervention regimen.
- 2.1.1.4 Age \geq 18 years.
- 2.1.1.5 ECOG performance status \leq 2 (see [Appendix A](#)).
- 2.1.1.6 Known human immunodeficiency virus (HIV)-infected individuals must be on effective anti-retroviral therapy with undetectable viral load within 6 months.
- 2.1.1.7 Known chronic hepatitis B virus (HBV) infected individuals, must be on suppressive therapy with undetectable viral load.
- 2.1.1.8 Individuals with a history of hepatitis C virus (HCV) infection must have been treated and cured.
- 2.1.1.9 The effects of ¹⁸F-DCFPyL (study drug) on the developing human fetus are unknown. For this reason and because this agent as well as other therapeutic agents used in this trial are known to be teratogenic, women of child-bearing potential and men must agree to use adequate contraception (hormonal or barrier method of birth control; abstinence) prior to study entry and for 2 months after each study PET/CT imaging. Should a woman become pregnant or suspect she is pregnant while she or her partner is participating in this study, she should inform her treating physician immediately.
- 2.1.1.10 Ability of subject to understand and the willingness to sign a written informed consent document.

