3 STUDY IMPLEMENTATION

3.1 STUDY DESIGN

This is an open-label multi-center study recruiting participants with suspected hepatocellular carcinoma (with at least one detectable liver lesion on standard of care CT and/or MRI) who are eligible to undergo local treatment for HCC (e.g., surgical resection, radiofrequency ablation, microwave ablation, transarterial embolization (TAE), stereotactic body radiotherapy (SBRT)). Participants will be consented and enrolled through the NIH Clinical Center.

All participants will undergo a baseline ¹⁸F-DCFPyL PET/CT. Within approximately 2 weeks of each ¹⁸F-DCFPyL PET/CT scan, participants will also be scanned with a ¹⁸F-FDG PET/CT imaging. ¹⁸F-FDG PET/CT may be performed within two weeks before or after each ¹⁸F-DCFPyL PET/CT scan. Each PET/CT imaging must be approximately a day apart. The order obtained for ¹⁸F-DCFPyL PET/CT and ¹⁸F-FDG PET/CT does not matter.

A CT and/or MRI will be performed within 2 months of the ¹⁸F-DCFPyL PET/CT scan. Clinical scans performed in this time frame by local providers are also acceptable.

Participants will undergo a biopsy prior to/concurrent with local therapy (more than one lesion may be biopsied during the same procedure). The procedure may be performed at the NIH Clinical Center or at the participating site (Washington DC Veteran's Affairs Medical Center). The treatment procedure will be scheduled as clinically indicated and samples will be collected prior to therapy (or during surgical resection).

An additional ¹⁸F-DCFPyL PET/CT imaging will be performed during the first routine post local therapy follow-up for participants with a positive baseline ¹⁸F-DCFPyL-PET/CT (i.e. the presence of DCFPyL-avid tumor/s) and with a biopsy confirming HCC diagnosis. Subjects with negative tumor uptake at the baseline ¹⁸F-DCFPyL-PET/CT and with a biopsy confirming HCC, will not have study-related imaging post-treatment and will remain in follow-up. Subjects with biopsies negative for HCC will be taken off protocol.

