3.3 STUDY CALENDAR

Procedures	Screening ¹	Baseline ¹ Study Visit 1	Study Visit 2 ¹⁰	Follow-up ¹¹	Disease Progression
Informed consent	X				
Medical Assessment					
Demographics	X				
Medical history	X				
Concomitant medication review	X				
Physical Assessment					
ECOG	X				
Physical exam (including height and weight)	X				
Vital signs	X	X 2	X 2		
Laboratory Assessment					
Hematology (CBC with diff and platelet)	X		X		
Serum chemistry/Acute Care Panel 3	X		X		
Serum or urine pregnancy test 4	X		X		X
Study Intervention					
CT and/or MRI	X 5		X 5		X 12
¹⁸ F-DCFPyL PET/CT imaging 6		X	X		X 12
¹⁸ F-FDG PET/CT imaging 7		X	X		X 12
Adverse Event Monitoring					
Injection site monitoring 8		X	X		X
Adverse event monitoring/Query 8		X	X		X

Procedures	Screening ¹	Baseline ¹ Study Visit 1	Study Visit 2 ¹⁰	Follow-up ¹¹	Disease Progression
Correlative studies					
Tumor marker tests 9, 13		X	X		X
Exome germline control blood collection		X			
Tumor Biopsy		Concurrent with standard of care therapy (pre-treatment or during surgical resection)			
Blood and urine for EVP analysis 13		X	X	X	X
Follow-up evaluations					
Review of clinical chart, phone call or e-mail (or any NIH approved platform)				X	
Collection/review of imaging scans				X	

1. Performed within 30 days prior to administration of ¹⁸F-DCFPyL unless otherwise indicated. Screening procedures such as medical assessment may be performed remotely via any NIH approved platforms.
2. Vital signs will be taken prior to injection of ¹⁸F-DCFPyL.
3. Acute care panel: sodium, potassium, chloride, total CO₂, creatinine, glucose, urea nitrogen, eGFR
4. For female participants of childbearing age (in the absence of prior hysterectomy). Pregnancy tests may be performed as clinically indicated prior to each scan.
5. CT (Chest/Abdomen/Pelvis) and/or MRI (Abdomen) will be performed within 2 months of each ¹⁸F-DCFPyL PET/CT. Imaging may be performed at certified outside facility and provided to study team.
6. Subjects will undergo ¹⁸F-DCFPyL injection and a dynamic PET/CT. Approximately 1 hour (+/- 10 minutes) post ¹⁸F-DCFPyL injection, a static PET/CT imaging performed. Refer to section **3.2.2** for additional information regarding the scanning procedure.
7. ¹⁸F-FDG PET/CT will be performed within approximately 2 weeks before or after each ¹⁸F-DCFPyL scan. Each PET/CT imaging must be approximately a day apart. The order obtained for ¹⁸F-DCFPyL PET/CT and ¹⁸F-FDG PET/CT does not matter.

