3.6.2 Off-Study Criteria

- Participants with biopsy that does not confirm HCC diagnosis
- Participant requests to be withdrawn from the study
- Participant becomes pregnant
- PI discretion
- Subject becomes decisionally impaired
- Lost to follow up
- Death
- PI decision to close the study
- Completion of follow up period
- Screen failure

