5.2.3 Analysis of Extracellular Vesicles and Particles (EVPs)

Blood and urine samples will be used in the [name] Lab (stored in [name] lab) for analysis of extracellular vesicles and particles (EVPs). Specifically, we are most interested in measuring the concentration and composition of the EVPs that are PSMA+ across the samples, as related to PSMA detection on imaging and in response to treatment. We have identified robust methods for detecting and isolating PSMA+ EVPs, and then evaluating co-expressed proteins and nucleic acids associated with those EVPs. EVPs in general will be processed and evaluated according to our published protocols (nano.ccr.cancer.gov), with PSMA+ EVPs enriched by immunoaffinity from cell-free blood and urine samples. Our hypothesis is that the molecular cargo and composition of the PSMA+ EVPs in liquid biopsies (ie, accessible in blood and urine samples) may correlate with 1) imaging extent of PSMA detection, 2) additional histopathologic features identified in the targeted biopsies in the study, and 3) the biological / clinical course of PSMA+ foci, followed over time, including, but not limited to, local control and time to progression.

The following analysis will be performed:

1. Isolation of EVPs will be performed with size exclusion and affinity chromatography.
2. Enumeration and characterization of EVPs and their composition will be performed with nanoparticle tracking analysis, resistive pulse sensing, and flow cytometry to determine whether volume of PSMA+ tissue on imaging correlates with concentration of PSMA+ EVPs in blood and/or urine. Routine laboratory assays for protein/DNA/RNA quantification will also be performed.

Where sufficient cell free biofluid is available, NGS DNA methylomics will be compared between pooled PSMA+ (or other surface marker positive) EVP vs PSMA- (marker negative) vs general biofluid isolates to identify distinctive EVP subset cargo signatures that correlate with disease extent, progression, or other clinical / histopathologic correlates.

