10.6 ANALYSIS OF THE SECONDARY ENDPOINTS

- The lesion level sensitivity, specificity and positive predictive value of ^{18}F -DCFPyL PET/CT and CT/MRI will be calculated and compared. The confidence interval for each estimate will be obtained from the bootstrap samples as described in **10.5** and the difference in the estimates between the imaging modalities will be compared by the Wald test with the standard error calculated from the bootstrap samples.
- For ^{18}F -DCFPyL PET/CT positive participants who undergo local treatment for HCC, change in ^{18}F -DCFPyL PET/CT uptake between pre- and post-treatment of tumor or tumor bed will be compared by paired Wilcoxon test.

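### The Wald tests of DCFPyL against CT/MRI in section 10.6 can reject through selection alone: CT/MRI selects every participant, and neither the biopsied lesions nor a CT/MRI positivity rule is specified

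*Combined protocol and SAP*

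**What the plan says.** All references are to the combined protocol and SAP.

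- **Aim.** Section 1.1.2 makes it the first secondary objective to compare the ability of DCFPyL PET/CT "to detect HCC with standard of care imaging (CT and/or MRI"), and with FDG PET/CT.
- **Entry.** Section 2.1.1 requires "High radiological suspicion of hepatocellular carcinoma (LR4 or LR5 based on the most current version of LI-RADS) with at least one measurable lesion" on CT and/or MRI.
- **Biopsy.** Section 3.1: "Participants will undergo a biopsy prior to/concurrent with local therapy (more than one lesion may be biopsied during the same procedure"). The study calendar (3.3) times it as "Concurrent with standard of care therapy (pre-treatment or during surgical resection"). Section 3.4 excludes surgery done only to obtain research tissue. Section 5.2.3 refers to "additional histopathologic features identified in the targeted biopsies in the study" without saying what they target.
- **Reference standard and positivity.** Section 10.1 relates DCFPyL-positive sites to histopathology. It defines DCFPyL positivity inside the liver (SUVmax above 1.2 times normal liver mean) and outside it. No section gives a matching rule for CT/MRI, or a reference standard for lesions without tissue.
- **Biopsy-negative participants.** Section 3.1: "Subjects with biopsies negative for HCC will be taken off protocol". Section 3.6.2 lists "Participants with biopsy that does not confirm HCC diagnosis" as an off-study criterion.
- **Analysis.** Section 10.6: "The lesion level sensitivity, specificity and positive predictive value of ^{18}F -DCFPyL PET/CT and CT/MRI will be calculated and compared", with Wald tests using bootstrap standard errors. Section 10.2 lists FDG as a second comparator; section 10.6 does not name it.

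**The concern.** A head-to-head accuracy comparison needs a lesion set that neither test has selected, or an adjustment for the selection. Here the comparator is also the entry test, so nobody without a suspicious CT/MRI lesion can enter. CT/MRI misses are under-represented, and so are its correct negatives. Its apparent sensitivity is pushed up and its apparent specificity down, while DCFPyL is not affected in the same way.

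Verification adds a second layer. If tissue comes mainly from CT/MRI-positive lesions, CT/MRI moves further towards 100% sensitivity and 0% specificity. If it comes mainly from DCFPyL-positive lesions, DCFPyL moves there instead. The plan does not say which applies, and the missing CT/MRI threshold leaves a further choice that could be made after the results are known. At stake is a formal significance statement on the first secondary objective that may reflect the design rather than the tracer.

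**Working it through.** **1. The plan's own figure.** Section 10.4 gives a half-width of 0.148 for PPV with 40 evaluable participants. Inputs: PPV 0.70, correlation 0.2, and 80% of 40 = 32 participants with one or two lesions. The mix of one and two is not stated. If 25% have two, there are 24 + 16 = 40 lesions. The design effect is 1 + ((24 + 8×4)/40 − 1)×0.2 = 1.08, and the half-width is 1.96×√(0.21×1.08/40) = 0.1476. The figure reproduces. No precision or power is given for the section 10.6 comparisons.

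**2. Entry selection alone, all lesions verified.** Assumptions: both modalities 75% sensitive and 75% specific, errors independent given disease, 70% of lesions HCC, correlation 0.2, half of participants with two lesions, and CT/MRI-positive meaning the kind of finding that permits entry.

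- Two-lesion participants: both HCC 0.49 + 0.2×0.21 = 0.532; discordant 2×0.21×0.8 = 0.336; neither 0.132.
- Probability of entry (at least one CT/MRI-positive lesion): 1 − 0.25² = 0.9375; 1 − 0.25×0.75 = 0.8125; 1 − 0.75² = 0.4375.
- HCC lesions entering: one-lesion 0.7×0.75 = 0.525; two-lesion 2×0.532×0.9375 + 0.336×0.8125 = 1.2705. CT/MRI-positive among them: 0.525 and 1.4×0.75 = 1.05.
- Apparent CT/MRI sensitivity: (0.525 + 1.05)/(0.525 + 1.2705) = **0.877**, against a true 0.75.
- Non-HCC lesions entering: 0.3×0.25 = 0.075, and 0.336×0.8125 + 2×0.132×0.4375 = 0.3885. CT/MRI-positive among them: 0.075 and 0.6×0.25 = 0.15.
- Apparent CT/MRI specificity: 1 − 0.225/0.4635 = **0.515**, against a true 0.75.

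DCFPyL keeps 0.75 and 0.75. The distortion grows as fewer participants have two lesions. With one lesion each, CT/MRI is 100%/0% by construction.

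**3. Rejection rates when there is no true difference.** Simulation of 40 participants under the same assumptions, with a participant bootstrap taken with replacement (400 trials per row, 300 resamples):

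| Scenario | Sensitivity | Specificity | PPV |
|---|---|---|---|
| No CT/MRI selection, all verified | 7% | 8% | 8% |
| CT/MRI selects, all verified | 41% | 27% | 15% |
| CT/MRI selects, positive on either verified | 43% | 32% | 17% |
| CT/MRI selects, only CT/MRI-positive verified | 99.8% | 72% | 51% |

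A second set of simulations at 75%/75% gave 26-62% (sensitivity) and 16-39% (specificity) for the second row, about 99% and 70-77% for the last, and 5-8% without selection. With both modalities at 85%/70% or 90%/80%, the second row gives 19% or 18% for sensitivity and 30% or 25% for specificity. The direction is unchanged.

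**4. Biopsy led by DCFPyL.** If only DCFPyL-positive lesions are verified, DCFPyL is 100%/0% by construction. Given independence, CT/MRI keeps the step 2 values. Two equal tests then differ by 1 − 0.877 = +0.12 in sensitivity and 0 − 0.515 = −0.51 in specificity.

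**5. PPV.** Separate assumptions: 50% HCC, CT/MRI 85%/80%, independence, only CT/MRI-positive lesions verified.

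- CT/MRI PPV: 0.425/(0.425 + 0.10) = 0.810.
- Equal tracer: 0.36125/(0.36125 + 0.02) = 0.948, an apparent +0.138 when the truth is 0. At half-maximal dependence between modalities this is +0.058, and at full dependence 0. Under DCFPyL-led sampling it becomes −0.138.
- Tracer with 60% specificity: 0.36125/(0.36125 + 0.04) = 0.900, an apparent +0.091. Its true PPV is 0.425/0.625 = 0.680, a true difference of −0.130. With 25% of DCFPyL-only lesions verified the apparent difference is +0.015; at about 31% it reaches zero; at 50% it is −0.043.

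**6. Threshold.** Assume 28 HCC and 12 non-HCC lesions, one per participant, and a tracer with 80% sensitivity. If LR4 and LR5 both count as positive, CT/MRI is 28/28. The Wald test then rejects at four or more DCFPyL misses, with probability P(Bin(28, 0.2) ≥ 4) = 0.84. If only LR5 counts and 5 HCC and 5 non-HCC lesions are LR4, CT/MRI is 23/28 = 82% and 5/12 = 42%, and the simulated rate falls to about 1%. This shows only how much the unstated rule matters, since no true CT/MRI accuracy is assumed.

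**The case against.** **The direction is unknown.** This stands. Section 10.1 starts from DCFPyL-positive sites, section 10.4 counts lesions identified by DCFPyL, and resection can also supply histology. A reader might infer that CT/MRI will show 100% sensitivity and 0% specificity and that the comparison is stacked against DCFPyL. The documents do not support that; it follows only if every verified lesion is CT/MRI-positive. The point does not need it, because the second row of the step 3 table assumes complete verification.

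**LR4/LR5 is the implied CT/MRI threshold.** It may be what was meant, but it appears only as an entry criterion. Adopting it makes every participant CT/MRI-positive, which is the selection problem itself. It also leaves extrahepatic lesions without a rule.

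**Section 10.1 may intend histology for every DCFPyL-positive site.** It does not require this, and entry selection would remain.

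**The sizes rest on assumptions.** They do. In particular, the PPV sign reversal disappears once about 31% of DCFPyL-only lesions are verified, and the PPV bias shrinks as the modalities agree more.

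**Biopsy-negative participants.** A reader might infer from sections 3.1 and 3.6.2 that their lesions drop out and that specificity loses its denominator. The documents do not say so. Leaving the study follows baseline imaging and biopsy, no section deletes data, Visit 2 is not required of these participants, and the 70% PPV in section 10.4 presupposes that non-HCC lesions count. A line of confirmation is enough.

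**It is a secondary comparison in a study sized for precision.** True, and this limits the severity. It is still the first secondary objective, and a formal test is attached to it.

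**Conclusion.** The concern holds in this form: followed as written, the section 10.6 tests of sensitivity and specificity against CT/MRI can declare a difference between equally accurate modalities. Under the 75%/75% assumptions the rates are about 26-62% and 16-39% with every lesion verified, and about 99% and 70-77% if only CT/MRI-positive lesions are biopsied. More complete verification alone does not cure this, because entry selection remains. The direction of any further bias depends on a biopsy rule that the plan does not state. The PPV contrast is conditional on sampling, and neither its size nor its sign can be fixed from the documents.

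Accuracy, prevalence (apart from borrowing the plan's 70% PPV), independence between modalities and the lesion mix are assumptions, so the sizes are illustrations. The direction of the entry-selection effect did not change over the accuracies tried. All bootstrap figures use resampling with replacement. Section 10.5 says without replacement; at full sample size that returns the same data and a zero standard error, which is a separate matter.

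This should be changed before analysis. It does not touch the primary endpoint estimate.

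**What to change.** In section 10.6:

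1. Replace the Wald tests of sensitivity and specificity against CT/MRI with descriptive estimates and confidence intervals, labelled as conditional on CT/MRI-selected participants and on the lesions actually biopsied.
2. Report PPV beside HCC prevalence among biopsied lesions, split by whether CT/MRI, DCFPyL or both identified the lesion. Do not present it as unconditional head-to-head accuracy.
3. Fix the CT/MRI positivity rule before analysis, including one for extrahepatic lesions. Record which modality identified each biopsied lesion, count unverified DCFPyL-only lesions, and confirm that biopsied lesions of participants taken off study for a non-HCC biopsy stay in the analysis.
4. Add the DCFPyL-versus-FDG comparison from section 10.2 on the same biopsied lesions. State that it favours DCFPyL if DCFPyL guided the biopsy and that power is limited. By simulation with assumed inputs, power is about 70% for sensitivity 80% versus 50% on 28 HCC lesions (90% for 80% versus 40%), but only about 22% for a 20-point specificity difference on 12 non-HCC lesions and 13% on 5.

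**Cost.** SAP wording, one field per biopsied lesion and one count. FDG scans are already scheduled and the LI-RADS category is assessed at entry. The claim against CT/MRI narrows to a conditional, descriptive one. No biopsy practice changes.

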8. Event monitoring will be done at the time of injection, and 1 hour post injection. All subjects will be contacted by phone at ~1-3 business days post-injection and will be asked non-leading questions regarding symptoms. At the investigator's discretion, subjects

with safety concerns noted during the post injection period may remain at the site or be asked to return to the site to undergo further safety assessments at the 1-3 business day follow-up time point.

9. Tumor markers include Alpha-fetoprotein, carcinoembryonic antigen, carbohydrate antigen 19.9 (CA19.9) and liver function tests (Alkaline Phosphatase, ALT, AST, Total Bilirubin, Direct Bilirubin). Refer to section **5.1** for more details.
10. Only participants with a positive baseline ¹⁸F-DCFPyL-PET/CT scan (i.e. with the presence of DCFPyL-avid tumor/s) and a biopsy confirming HCC diagnosis will undergo visit 2 for a second ¹⁸F-DCFPyL PET/CT (during routine treatment follow up, typically within 16 weeks).
11. Follow-up will be performed every 3 months (\pm 2 weeks) after the last ¹⁸F-DCFPyL scan (or after therapy for participants with negative baseline ¹⁸F-DCFPyL PET/CT and biopsy confirming HCC) for 2 years, and yearly afterwards for an additional 3 years.
12. If tumor recurrence occurs during the follow-up period, an ¹⁸F-DCFPyL PET/CT, ¹⁸F-FDG PET/CT, CT/MRI and biopsy may be performed any time after recurrence at PI discretion. Biopsy would be performed concurrently with treatment if the latter is performed.
13. Blood collection for tumor markers and EVP analysis may be omitted beyond visit 2 if any issues with scheduling or logistics. The same applies to urine collection for EVP analysis.

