6.3.1.1 Image Analysis

Target Lesions: Images will be analyzed by MIB staff by identifying, recording and measuring measurable target lesions. A segmentation tool will be applied to generate semi-automated volume of interests (VOI) within the target lesion(s). Maximum standardized uptake value (SUV_{max}) and tumor volumes will be extracted from the generated target lesion(s) VOIs. ^{18}F -DCFPyL uptake in major organs and bone marrow will also be measured and mean SUV values will be extracted.

All other lesions (or sites of disease) including any measurable lesions should be identified as non-target lesions and should also be recorded.

Antitumor effect: To determine whether uptake of ^{18}F -DCFPyL correlates with response to therapy, target tumor(s) imaging PET parameters, including SUV_{max} , and tumor volume will be compared between responders vs non-responders. Participant response will be based on RECIST 1.1. criteria and clinical assessment.

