10.2 SECONDARY ENDPOINTS

- Compare the lesion level sensitivity, specificity and positive predictive value of ¹⁸F-DCFPyL PET/CT with standard CT and/or MRI imaging, and ¹⁸F-FDG PET/CT.
- Compare ¹⁸F-DCFPyL PET/CT uptake between pre- and post-treatment in ¹⁸F-DCFPyL PET/CT positive participants (as measured by change in pre-treatment and post-treatment SUV) to detect treatment response following local treatment.

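### Section 10.6 tests whether uptake changes after local therapy, not whether the change identifies response, and the responder comparison in 6.3.1.1 never reaches section 10

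*Combined protocol and SAP*

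**What the plan says.** All references are to the combined protocol and SAP.

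- **Objective (1.1.2).** The second secondary objective concerns the ability of 18F-DCFPyL "PET/CT imaging to assess treatment response to local therapy".
- **Endpoint (10.2).** The endpoint is the SUV change from before to after treatment in PET-positive participants, used "to detect treatment response following local treatment".
- **Analysis (10.6).** The change in uptake "of tumor or tumor bed will be compared by paired Wilcoxon test". Nothing else is given for this objective.
- **Image analysis (6.3.1.1).** To see whether uptake correlates with response, target-tumor PET parameters including SUVmax and "tumor volume will be compared between responders vs non-responders". On the reference: "Participant response will be based on RECIST 1.1. criteria and clinical assessment".
- **Who is rescanned (3.3, footnote 10).** Only someone with an avid tumor at baseline and "a biopsy confirming HCC diagnosis will undergo visit 2 for a second" PET/CT.
- **Anatomic imaging (3.3, footnote 5).** "CT (Chest/Abdomen/Pelvis) and/or MRI (Abdomen) will be performed within 2 months of each" study PET/CT, so CT/MRI is already scheduled at Visit 2.

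Sections 10.3 and 10.7 relate uptake to 5-year progression-free and overall survival. They do not mention response to local therapy.

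**The concern.** The objective asks whether the scan tells responders from non-responders. The paired Wilcoxon asks whether uptake is, on the whole, different after treatment from before it.

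The gap matters in this population because local therapy includes surgical resection and 10.6 measures tumor or tumor bed. Where the lesion has been removed, uptake at that site can fall because the tissue is gone. Since 10.2 attaches detection of response to the change in SUV, a small p-value from the paired test could be reported as support for the objective when it shows only that treated sites take up less tracer.

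The comparison that could separate these cases is mentioned in 6.3.1.1 but has no analysis in section 10. Several choices would therefore be made after the data are seen: baseline value or change, which categories count as response, and when response is read.

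**Working it through.** **1. The passages side by side**

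| Element | 6.3.1.1 | 10.2 | 10.6 |
|---|---|---|---|
| PET measure | SUVmax, tumor volume | change in SUV, type not stated | uptake, pre and post |
| Response variable | RECIST 1.1 and clinical assessment | none | none |
| Baseline or change | not stated | change | change |
| When response is read | not stated | not stated | not applicable |
| Test or estimate | none named | not applicable | paired Wilcoxon |

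6.3.1.1 also gives no rule for combining RECIST with clinical assessment, no list of the categories that count as response, and no classification for a participant whose lesion was resected.

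**2. How many participants could contribute**

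The plan states no N, power or effect size for this objective, so there is no figure to reproduce. The inputs below come from 10.4, where they serve the primary endpoint.

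- PET-positive: 40 x 0.80 = 32.
- One lesion each, with the 70% lesion-level PPV as a proxy for biopsy confirmation: 32 x 0.70 = 22.4.
- Two lesions each, correlation 0.2: P(at least one is HCC) = 1 - (0.3^2 + 0.2 x 0.7 x 0.3) = 1 - (0.090 + 0.042) = 0.868, and 32 x 0.868 = 27.8.

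The working range is therefore 22 to 28. It is an assumption, because a lesion-level PPV is not a participant-level confirmation rate. If every PET-positive participant were confirmed, it would be 32. A lower case of 15 with a usable response reading is also assumed.

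**3. What the paired test cannot separate**

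Suppose uptake falls by 0.8 SD of the within-person change in everyone, whatever the response. In 4,000 simulated trials the paired Wilcoxon gave p<0.05 in 93% at n = 22 and 97% at n = 28. An exact rank-sum test of responders against non-responders on the same data rejected in 4-5%. This follows by construction and only illustrates the logic.

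**4. Precision of the missing comparison**

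Take a 1 SD difference in change between the groups: AUC = Phi(1/sqrt 2) = 0.760. The Hanley-McNeil variance, with k non-responders and m responders, is

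[A(1-A) + (k-1)(Q1-A^2) + (m-1)(Q2-A^2)] / (km), where Q1 = A/(2-A) = 0.6132, Q2 = 2A^2/(1+A) = 0.6567 and A^2 = 0.5780.

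- n = 15, k = 3: (0.1823 + 2 x 0.0352 + 11 x 0.0787)/36 = 0.0311, SE 0.176. The symmetric upper limit is 0.76 + 1.96 x 0.176 = 1.11, above 1, so the logit scale is used: 1.154 +/- 1.96 x 0.176/0.1823, giving 0.32-0.95.
- n = 28, k = 13: (0.1823 + 12 x 0.0352 + 14 x 0.0787)/195 = 0.0088, SE 0.094, giving 0.54-0.90.

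| n | Non-responders (assumed) | Logit 95% interval | Rank-sum power, 1 SD |
|---|---|---|---|
| 15 | 3 / 5 / 7 | 0.32-0.95 / 0.40-0.94 / 0.44-0.93 | 27 / 33 / 38% |
| 22 | 4 / 7 / 10 | 0.39-0.94 / 0.47-0.92 / 0.50-0.91 | 36 / 51 / 54% |
| 28 | 6 / 9 / 13 | 0.46-0.92 / 0.51-0.91 / 0.54-0.90 | 50 / 63 / 68% |

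**5. Choice of interval**

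In a smaller simulation (600 trials, 300 resamples, 1 SD difference) the 95% percentile bootstrap covered the true AUC in 83% (n = 15, 3 non-responders), 90% (n = 15, 5) and 89% (n = 22, 4). At n = 15 with 3 non-responders, about 5% of samples separated perfectly. The bootstrap interval then collapses to a point and the plain logit is undefined.

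**The case against.** The paired Wilcoxon matches the endpoint that 10.2 defines, a change in SUV, and is a sound test of it. No document makes p<0.05 a success criterion for this objective, so the harm depends on how the result is later described. 6.3.1.1 names the parameters and the reference, and a time point can be inferred: Visit 2, typically within 16 weeks, with CT/MRI within 2 months of the scan. The added comparison would be weak, and its reference is doubtful after local therapy; section 1.3.2 itself notes that radiologic appearance and biologic activity do not correlate well.

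Much of this stands. It limits the size of the point and rules out a pass/fail test. It does not remove the gap, because nothing ties the Visit 2 imaging to a response classification, and imprecision is no reason to leave the measure and the definition open.

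Three stronger readings are tempting and are not supported:

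- A reader might infer that the 93-97% is a false-positive rate. It is power against a real fall in uptake.
- A reader might infer that the plan never considers responders. 6.3.1.1 does.
- A reader might infer that 6.3.1.1 already specifies the comparison of change. Its text could equally mean that baseline uptake predicts response, which is a different question.

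**Conclusion.** The point holds as a mismatch between objective and analysis. Followed as written, section 10 can show that uptake changed after local therapy. It cannot show that the change identifies response, which is the use 10.2 makes of it. This rests on the text alone and needs none of the simulated figures. Those illustrate the logic and do not measure an error rate in this trial.

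The sample sizes, non-responder counts and the 1 SD difference are assumptions, and they matter only for judging how precise the added estimate would be. The objective is secondary and the primary PPV analysis is untouched, so this should be corrected but does not threaten the trial. How tumor-bed uptake is measured is also unstated, but that is missing detail rather than part of this conclusion.

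**What to change.** 1. In 10.6, state that the paired Wilcoxon is evidence of change in uptake only. Report the change separately for resected participants and for those given other local therapy, with everyone kept in the overall analysis.
2. Add to 10.2 and 10.6 a comparison of participant-level change in SUVmax between responders and non-responders, with a rule for participants who have more than one lesion. If 6.3.1.1 intends baseline uptake as a predictor of response, list that as a separate analysis.
3. Define the response variable: which RECIST 1.1 categories at Visit 2 count as response, how RECIST and clinical assessment are combined when they disagree, and how resected participants are classified for this analysis.
4. Report the AUC as an estimate with a small-sample 95% interval, either score-type or logit with a stated rule for perfect separation. Do not use the percentile bootstrap here.
5. Treat tumor volume as secondary, because it partly overlaps a size-based reference.

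**Cost.** This is analysis wording plus a response definition, to be settled before PET change is set against response. It needs no new visits, scans or participants. The price is an imprecise estimate against an imperfect reference, so disagreement with RECIST should not be read as proof that the PET is wrong.
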